## STATEMENT OF COMPLIANCE

[The trial will be carried out in accordance with International Council on Harmonisation Good Clinical Practice (ICH GCP) and the following:

- United States (US) Code of Federal Regulations (CFR) applicable to clinical studies (45 CFR Part 46, 21 CFR Part 50, 21 CFR Part 56, 21 CFR Part 312, and/or 21 CFR Part 812).

National Institutes of Health (NIH)-funded investigators and clinical trial site staff who are responsible for the conduct, management, or oversight of NIH-funded clinical trials have completed Human Subjects Protection and ICH GCP Training.

The protocol, informed consent form(s), recruitment materials, and all participant materials will be submitted to the IRB for review and approval. Approval of both the protocol and the consent form(s) must be obtained before any participant is consented. Any amendment to the protocol will require review and approval by the IRB before the changes are implemented to the study. All changes to the consent form(s) will be IRB approved; a determination will be made regarding whether a new consent needs to be obtained from participants who provided consent, using a previously approved consent form.]

## 1 PROTOCOL SUMMARY

### 1.1 SYNOPSIS

**Title:**

TEEN HEED: An Adolescent Peer Led Diabetes Prevention Intervention

**Grant Number:**

<Grant Number>

**Study Description:**

Specific Aims: 1) Explore strategies for using peer educators and novel mobile health technologies as part of a group lifestyle change program for diabetes prevention among at-risk ethnic minority youth in a New York City community with high disease burden. 2) Refine, implement, and evaluate outcomes for the intervention. Using preliminary data, we will use CBPR to refine our developmentally and culturally appropriate lifestyle intervention for pre-diabetic ethnic minority adolescents. We will then screen at-risk adolescents for pre-diabetes and related lifestyle and biological measures and compare outcomes in adolescents in intervention and wait list control groups to test intervention effectiveness. 3) Further refine the intervention for a larger RCT based on an examination of intervention feasibility, acceptability, and sustainability.

**Objectives\*:**

The specific aims of the TEEN HEED (Help Educate to Eliminate Diabetes) Trial are to:

1. Use an iterative process between academic and community partners to adapt and modify the pilot TEEN HEED intervention
2. Use qualitative methods to evaluate strategies for using peer educators and novel mobile health technologies as part of a group lifestyle change program for diabetes prevention among at-risk ethnic minority youth
3. Use community-based participatory research strategies to refine, test, and evaluate outcomes of a peer education diabetes prevention program for pre-diabetic ethnic minority adolescents.
4. Examine intervention feasibility, acceptability, and sustainability.

**Endpoints\*:**

**Evaluation of the intervention's impact on the primary study outcome, participants' weights:** We hypothesize that the TEEN HEED intervention will result in maintenance or decrease in BMI percentile.

Evaluation of the effectiveness of the TEEN HEED intervention on behaviors and mediators related to weight loss and diabetes prevention: We hypothesize that the intervention will lead to observable changes to diet, physical activity and weight control behaviors and that these and other mediators explain weight loss.

**Study Population:**

*This study involves adolescents ages 13-19.*

*N/A*

**Phase\* or Stage:**

**Description of Sites/Facilities Enrolling Participants:**

*All programming will be offered via Zoom. In-person study visits for baseline, 5m, and 12m, will be conducted at our pediatric clinic.*

**Description of Study Intervention/Experimental Manipulation:**

*12 week virtual workshop (offered via zoom) that covers behavioral skills including goal setting, self-monitoring, problem solving, contingency management, coping skills, and social support. Workshop topics included explanation of pre-diabetes/diabetes, label reading, healthy plate planning, portion control, finding affordable healthy foods, strategies to increase physical activity, and coping with eating triggers and social pressures. Participants create and report on action plans with weekly goals, brainstorm to solve problems, and communicate between sessions.*

**Study Duration\*:**

[figure not shown]
*3 years*

**Participant Duration:**

*12m*

**1.2 SCHEMA**

**Flow Diagram (e.g., randomized controlled trial)**

**1.3 SCHEDULE OF ACTIVITIES (VIRTUAL TEEN HEED)**

	Pre-screening (Pre-consent)	Visit 1 Baseline	12-week workshop	3m visit
EMR Review Eligibility	X			
Informed Consent		X		
Demographics		X		
Clinical history		X		
Height & Weight		X		X
Outcome Evaluation				
Workshop assessments/Action Planning			X	
Health and Lifestyle Questionnaire		X		X
Debrief session			X	
Adverse Events Reporting		X	X	X

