mPulse Mobile messaging programs follow compliance principles guided by Telephone Consumer Protection Act, Mobile Marketing Association's Consumer Best Practices, and CTIA Mobile Compliance Assurance Handbook. [name] will be the application manager.

All participants will also be advised about privacy issues surrounding responses to text messages. It will be recommended that they use a password to protect their cell phones. (Please see the previously submitted IT Security Risk Assessment Report).

We will be piloting the texting program with participants who had previously been enrolled in earlier version of the TEEN HEED study. We will obtain parental permission to allow mPulse Mobile to receive their cell phone numbers and send SMS text messages to participants. This information will be included in the study consent form with a separate place within the consent form for parents to initial to give this permission. Participants aged 18-19 will be asked to sign their own permission to receive SMS text messages from mPulse Mobile. We will make it very clear to participants that what is shared through the mobile dialogue is private, secure, and not shared with anyone beyond the program. We will also express that standard data and messaging rates from participant's provider may apply and that they can request that messages stop being sent at any time.

We will also conduct audio-recorded debriefing sessions with participants and peer leaders in which we will ask about their experiences with the intervention, reactions to the intervention, and ideas for intervention refinement. To monitor the community-academic partnership, we are tracking activities such as the communication between community-academic partners, number of participants at CAB meetings, number of manuscripts and presentations by academic-community partners, and policy-related outcomes. Additionally, we are investigating youth involvement in CBPR, through audio-recorded one-on-one interviews and qualitative analysis. This will help us understand how young people have helped shape the project. We are interviewing study participants, peer leaders, community action board members, interns, and study coordinators. They are being consented and asked questions about their personal experience with the study and their views on how young people have contributed to the project and how they may continue to do so in the future.

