#### 6.1.2 ADMINISTRATION AND/OR DOSING

Full-Dose: Attendance to all 12 workshops

Half-dose: Attendance to 6-11 workshops

Participants attending less than 4 workshops will be considered as "not adhering to the project"; however, they will not be removed from the study.

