### 7 STUDY INTERVENTION/EXPERIMENTAL MANIPULATION DISCONTINUATION AND PARTICIPANT DISCONTINUATION/WITHDRAWAL

#### 7.1 DISCONTINUATION OF STUDY INTERVENTION/EXPERIMENTAL MANIPULATION

When a subject discontinues from the study intervention (12-week workshop) but not from the study, remaining study procedures will be completed as indicated by the study protocol. If a clinically significant finding is identified (including, but not limited to changes from baseline) after enrollment, the investigator or qualified designee will determine if any change in participant management is needed.

The data to be collected at the time of study intervention discontinuation will include the following:

- The reason(s) for discontinuing the participant from the intervention, and methods for determining the need to discontinue
- If the participant is due to complete assessments within 2 weeks of being discontinued from the study intervention, those assessments will be administered at the time of discontinuation; if the next scheduled assessments are more than 2 weeks from the discontinuation date, the discontinued participant will wait for the next scheduled assessment. Thereafter, the participant will be included in all future scheduled assessments, even though not participating in the intervention.

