## 7.2 PARTICIPANT DISCONTINUATION/WITHDRAWAL FROM THE STUDY

Participants are free to withdraw from participation in the study at any time upon request.

An investigator may discontinue a participant from the study for the following reasons:

- Significant study intervention non-compliance, unless varying compliance is an aspect of the study objectives
- Lost-to-follow up; unable to contact subject (see **Section 7.3, Lost to Follow-Up**)
- Any event or medical condition or situation occurs such that continued collection of follow-up study data would not be in the best interest of the participant or might require an additional treatment that would confound the interpretation of the study
- The participant meets an exclusion criterion (either newly developed or not previously recognized) that precludes further study participation

Subjects who sign the informed consent form, and subsequently withdraw, or are discontinued from the study, will not be replaced.

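### The only scheduled debrief falls within the 12-week workshop period and none is listed at the 3m visit, so the evidence on acceptability may over-represent teens who kept attending.

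*Combined protocol and SAP*

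**What the plan says.** All references are to the combined protocol and SAP.

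- **Objective.** The fourth objective in the synopsis is: "Examine intervention feasibility, acceptability, and sustainability". The third specific aim uses that examination to refine the program for a larger RCT.
- **Timing of the debrief.** In section 1.3 the row "Debrief session" has a single X, in the 12-week workshop column. The 3m visit column has height and weight, the Health and Lifestyle Questionnaire and adverse events.
- **Who is debriefed.** Section 4.1: "We will also conduct audio-recorded debriefing sessions with participants and peer leaders in which we will ask about their experiences with the intervention". The same sentence adds reactions to the program and suggestions for improving it. It gives no week and does not restrict the sessions to those still attending.
- **Teens who stop the workshop.** Section 7.1 opens: "When a subject discontinues from the study intervention (12-week workshop) but not from the study, remaining study procedures will be completed as indicated by the" protocol. It records "The reason(s) for discontinuing the participant from the intervention, and methods for determining the need to discontinue", and says that after stopping "the participant will be included in all future scheduled assessments, even though not participating in the intervention".
- **Teens who attend little.** Section 6.1.2 labels those attending fewer than 4 workshops as not adhering; "however, they will not be removed from the study".
- **Removal.** Section 7.2 allows the investigator to discontinue a participant from the study for: "Significant study intervention non-compliance, unless varying compliance is an aspect of the study objectives".

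**The concern.** The teens who can best say why the program did not suit them are those who stopped coming. The one scheduled activity described as asking about experience, reactions and improvements sits in the period when they are, by definition, absent from sessions. The visit that they are expected to attend lists no equivalent.

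If the views collected come mainly from attenders, they are likely to be more favorable than those of everyone offered the program, and they will contain few of the reasons for leaving. The rationale in section 2.1 names keeping youth engaged as a known difficulty, and section 4.1 chooses virtual delivery partly to improve attendance. Information from disengaged teens therefore bears directly on the refinement that this study is meant to support.

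**Working it through.** The documents state no figure on debriefing or acceptability, so there is nothing to reproduce. The check is mainly a reading of the sections against each other.

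**Step 1: which steps could reach a teen who has stopped attending?**

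| Step | Section | Reaches a teen who stopped? |
|---|---|---|
| Debrief | 1.3, 4.1 | Not excluded, but placed in the workshop period, with no week and no method of reaching absent teens |
| Remaining procedures | 7.1 | Possibly covers the debrief, but the section does not say that it does |
| Reason for discontinuing | 7.1 | Yes, if discontinuation is formally recorded; gives a reason, not a view of the program |
| 3m visit | 1.3, 7.1 | Yes, but no debrief or acceptability item is listed |
| One-on-one interviews | 4.1 | Possibly; the main topic is youth involvement in the participatory research, and how interviewees are chosen is not stated |
| Usability testing and analytics | 4.1 | Covers the virtual and mobile components; not tied to teens who stop or to their reasons |

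**Step 2: the teen who drifts away.** A teen who attends two or three sessions and never formally stops is kept in the study by section 6.1.2. The discontinuation record in section 7.1 may never be triggered. Section 6.4 (adherence) is an empty heading, and no other section records why sessions were missed.

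**Step 3: the denominator.** No acceptability measure is named, and section 9.3 (populations for analyses) is empty. Nothing would show a reader how many of those offered the workshop had been heard.

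**Step 4: what selection could do, as a hypothetical only.** Let s be the share of offered teens who are heard and p the share of those who find the program acceptable. With no information on the rest, overall acceptability lies between s × p and s × p + (1 − s), so the width is 1 − s. Take p = 0.90, an assumption with no source in the documents.

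- s = 0.73: lower 0.73 × 0.90 = 0.657; upper 0.657 + 0.27 = 0.927; width 27 points.
- s = 9/19 = 0.474: lower 0.474 × 0.90 = 0.426; upper 0.426 + 0.526 = 0.953 (unrounded inputs); width 53 points.

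Both values of s are borrowed from section 2.2 and neither measures what is needed. The 73% is retention at the 5 and 12 month follow-up in an earlier cohort, not workshop attendance. The 9 are first-pilot teens who completed at least 4 of 8 sessions, set against 19 diagnosed with pre-diabetes; the number who started is not given. The ranges show how much is left open when a group is not heard. They do not show that this plan will miss that group.

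**The case against.** A reader might infer that teens who stopped are not asked at all, and that acceptability will be estimated only from those who stayed. The documents do not support either statement. The column in section 1.3 is a time period, not an attendance condition. Section 4.1 plans debriefing with participants, without restriction, and low attenders remain participants. The opening rule of section 7.1 can fairly be read to include the debrief among the remaining procedures. Section 7.1 also records reasons for formal discontinuation, and section 4.1 plans interviews that touch on personal experience. The items of the Health and Lifestyle Questionnaire are not in the documents, so it may already ask about the program.

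A second objection is that the debrief is audio-recorded qualitative work and no acceptability percentage is planned, so there is no estimate to be biased. This stands against any claimed numerical bias. It does not remove the issue, because qualitative findings also depend on whose views are collected.

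A third is that asking at the 3m visit cannot reach teens who do not return. That is correct, and it limits what the fix can achieve. A debrief late in the workshop and the 3m visit may also fall close together. The gain from the 3m visit is therefore not a later date: it is a contact that section 7.1 already requires for teens who have stopped the workshop.

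**Conclusion.** The point holds as a gap in planned data collection. The only scheduled debrief is in the workshop period, the 3m visit lists none, and no later scheduled step is stated to collect the views of teens who stopped attending. For those who drift away without formal discontinuation, no step is stated to collect their reasons either. The evidence on acceptability may therefore over-represent attenders.

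It does not extend to saying that these teens are excluded, or that the result is biased by a known amount. The size cannot be derived from the documents: they give no attendance figure for this program, no acceptability measure and no planned percentage. The ranges of 27 and 53 points are hypothetical.

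The conclusion assumes that section 1.3 is the full list of scheduled activities and that the existing questionnaire does not already contain program-feedback items. The synopsis also mentions 5m and 12m visits, but no section lists their activities, so they do not change the reading.

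**What to change.** 1. In section 1.3, add a short fixed set of acceptability items and the main reason for missed sessions to the 3m visit questionnaire. Give it to every teen who was offered the workshop, whatever their attendance.
2. In section 7.1, state that the debrief counts as a remaining procedure for teens who stop the workshop, so that sections 1.3, 4.1 and 7.1 agree. Say how absent teens will be contacted for it.
3. In section 9.4, report these items and the number debriefed by attendance level, with the number responding out of all offered the workshop, so that teens who are lost, withdrawn or removed are visible. The bands in section 6.1.2 (12, 6 to 11, fewer than 4) leave 4 and 5 sessions without a label, so the report should show the number of sessions attended.

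The cost is about five items at a visit already planned, a sentence or two in section 7.1 and one table. No new visit is needed. Teens lost to follow-up will still not be heard, but their number will be shown.

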## 2 INTRODUCTION

### 2.1 STUDY RATIONALE

The number of youth with type 2 diabetes in the U.S. is projected to increase by 49 percent by 2050, with higher rates among minority youth. The Diabetes Prevention Program (DPP) is recognized as a sentinel study demonstrating the effectiveness of lifestyle interventions for diabetes prevention among pre-diabetic adults but has not yet been replicated in youth. In addition, such intensive interventions are often not sustainable in high risk communities with limited resources. One strategy that has been successfully employed in adults from such communities is peer based health education. Research suggests that like adults, young people are more likely to hear and personalize messages, and thus to change their attitudes and behaviors, if they believe the messenger is similar to them and faces the same concerns and pressures. However, there have been no peer led interventions in ethnic minority teens and no interventions focused specifically on weight loss for diabetes prevention. Finally, another challenge identified in existing youth health intervention programs is keeping youth engaged to enhance program participation and impact. One potential strategy is the use of mobile technologies (text messaging, mobile applications, social media) to support weight management programs, but to date use of such technologies has not been studied in youth. This study's overall objective is to use community-based participatory research (CBPR) to develop and pilot test a youth peer-led diabetes prevention intervention incorporating novel mobile health technologies for at-risk adolescents in a vulnerable New York City community. The central hypothesis is that such an intervention will lead to maintenance or decrease in BMI, improved dietary, physical activity and weight control behaviors, and decrease in diabetes risk.

### 2.2 BACKGROUND

*Our Previous Study:* People who develop diabetes go through a period when they have “pre-diabetes,” defined by the American Diabetes Association as fasting blood glucose of 100-125 mg/dl, and/or 2-hour post-prandial blood glucose of 140-199 mg/dl, and/or hemoglobin A1c of 5.7-6.4%. Diabetes and pre-diabetes are being diagnosed more in children, likely related to increasing rates of obesity. National estimates are that about 16% of all adolescents have pre-diabetes with higher rates in obese adolescents or those with a family history of diabetes.

Weight loss is the single therapy proven to prevent diabetes. In clinical settings, overweight adults with pre-diabetes who reduce their weight by 5-10% can reduce their risk of developing diabetes by 55-60%. While there have been no large diabetes prevention trials in children and adolescents, school based, clinic-based and community-based trials have led to reduction in diabetes risk (improvements in body measurements and glucose or insulin levels) with intensive lifestyle interventions.

An effective low-resource diabetes prevention strategy devised for adults in high-risk communities is the use of peer leaders to promote lifestyle change. Investigators from the adult HEED study (GCO#05-0463) conducted a randomized-controlled trial to compare the effectiveness of peer-led community-based workshops, versus usual care (delayed intervention) in achieving weight

loss and prevention of diabetes among overweight (BMI > 25) adults with pre-diabetes in East Harlem. Over 400 adults with pre-diabetes were identified through the standard protocol for pre-diabetes screening, an oral glucose tolerance test (OGTT) (a fingerstick test with an instant read glucose analyzer). The OGTT is performed by measurement of glucose, both at fasting and after administration of a 75 gram oral glucose load. Adults with pre-diabetes were randomized to intervention and delayed intervention groups to test the effectiveness of the HEED intervention. Pre-diabetics in the intervention group had statistically significant weight loss maintained at one year and a leveling of their glucoses, as compared with controls.

Research suggests that like adults, young people are more likely to hear and personalize messages, and thus to change their attitudes and behaviors, if they believe the messenger is similar to them and faces the same concerns and pressures. However, relatively few studies have focused on peer led lifestyle interventions in youth. In the first pilot phase of the TEEN HEED intervention (GCO # 11-1711), we adapted the HEED intervention for East Harlem adolescents. We conducted community based screening for pre-diabetes among 56 at-risk obese adolescents. We measured glucoses using oral glucose tolerance tests. Adolescents completed a survey to assess diet and physical activity knowledge, attitudes and behaviors and diabetes risk. They also underwent detailed body measurements (i.e. height, weight, body fat, waist circumference) and blood pressure testing.

Nineteen adolescents diagnosed with pre-diabetes had more detailed assessment of their dietary intake and physical activity levels. Pre-diabetic adolescents were then invited to take part in an initial version of the TEEN HEED intervention. Trained adolescent peer educators partnered with experienced adult HEED workshop leaders to run the workshops. At follow up, participants again completed the oral glucose tolerance test, verbally administered questionnaire, body measurements (i.e. height, weight, body fat, waist circumference) and blood pressure testing. Out of 9 adolescents who completed at least 4 out of 8 workshop sessions led by trained teens, 5 had decreased BMI and 5 no longer had pre-diabetes at 3 month follow up.

To supplement what we have learned through the pilot study, we completed additional qualitative studies to further develop our intervention. We conducted focus groups to explore 1) peer influences on eating behaviors, physical activity, and other individual factors related to weight management, 2) strategies for further adapting our peer education diabetes prevention intervention for urban minority adolescents, and 3) use of mobile technologies (such as text messaging, mobile applications and social media) as an adjunct to the peer-led intervention.

We then recruited participants ages 13-19 who are at risk for diabetes through community youth organizations, health centers and schools, determined eligibility (overweight/obese by measured BMI), and invited them to return fasting for further evaluation. Those ages 13-17 required assent/parental consent, while those  $\geq 18$  signed their own consent. We screened teens for pre-diabetes using an oral glucose tolerance test (OGTT), obtained body measurements, blood pressure and metabolic tests, and administered a health and lifestyle survey. We screened 148 teens, of whom 90 were diagnosed with pre-diabetes (61%) and were randomized to intervention (n=41) and wait list control (n=49) groups. Each workshop group (10-15 teens) met for 90 minutes weekly for 12 weeks. All activities were delivered under the supervision of experienced adult health educators by youth peer leaders who underwent training including team building, group facilitation, and review of the workshop curriculum. We collected 5 and 12

month follow up data (73% retention at both time points). Information from this previous cohort will be used to refine our study.

In order to maximize the reach of this intervention, and with increasing need due to the pandemic, we are proposing a virtual component to the TEEN HEED program.

